6.2.25 Liver Function Abnormalities

Any subject meeting the following criteria will be identified and results will be listed separately for these subjects:

ALT or AST >3xULN or Bilirubin >2xULN

Where ALT = Alanine Aminotransferase, AST = Aspartate Aminotransferase, and ULN = Upper Limits of Normal.

6.3 Conventions

6.3.1 Medical Coding

Adverse events and medical history will be coded using the Medical Dictionary of Regulated Activities (MedDRA) Version 24.1 (or higher). Conditions will be assigned to a primary system organ class (SOC) and preferred term (PT) based on the Investigator-reported verbatim term.

Any medications taken (other than study drug) will be coded using the World Health Organization Drug Dictionary (WHO Drug) September 2021 Version (or higher). Medications (both prior and concomitant) will be assigned to an Anatomical Therapeutic Chemical (ATC) Level 3 drug classification and Preferred Name based on the medication name reported on the eCRF.

6.3.2 Data Handling

All clinical data programming will be performed using SAS® statistical software package (Statistical Analysis System, Version 9.4 or higher)^{Error! Reference source not found.} and based on Clinical Data Interchange Standards Consortium (CDISC) data standards.

Study Data Tabulation Model (SDTM) programming will follow SDTM version 1.7 together with SDTM implementation guide 3.3. Analytical Data Model (ADaM) programming will follow ADaM implementation guide 1.1. Specifications for SDTM and ADaM datasets are described in a separate document.

6.3.3 Validation Methods

All programming of datasets and outputs will be validated by independent programming (IP) of values, programmatic comparison and manual review of format compared to the SAP and agreed shell template. Figures will be validated by manual review of format and visual inspection of graphical display compared to tabulated data. Independent programming by a Statistician (Stat IP) will be performed for all analyses relating to the primary endpoint.

6.3.4 Descriptive Statistics

Continuous variables will be summarized by the number of non-missing observations, mean, median, standard deviation, and minimum and maximum.

Categorical variables will be summarized by presenting the frequency and percent. Percentages will be based on the number of non-missing observations or the subject population unless otherwise specified. For each variable, all categories will be shown. Zero frequencies (but not the percent) within a category will be presented.

Incidences of adverse events, medical history and concomitant medications will be reported at the subject level. Subjects can only be counted once within each PT and SOC under the highest severity and most related. Percentages will be calculated using the number of subjects in the treatment group for the Safety Population.

6.3.5 Decimal Places

Decimal places for derived data described in Section 6.2 will be determined by the scale of measurement unless otherwise stated. No decimal places will be displayed if the smallest calculated value is ≥ 100 ; 1 decimal place will be displayed when the smallest value is within the interval (10, 100), with 10 being inclusive; 2 decimal places will be displayed when the smallest value is within (1, 10), with 1 being inclusive; and so on for even smaller scales of measurement.

Derived data where it is known in advance the result will be an integer for example day, month, year, number of days and total scores (for rating scales) will be presented with zero decimal places.

For descriptive (summary) statistics, n will be reported as a whole number. Means, medians, and percentiles will be displayed to one more decimal place than the data, dispersion statistics (e.g., standard deviation) will have two more decimal places, and the minimum and maximum will be

displayed to the same number of decimal places as reported in the raw data. Percentages will be displayed with one decimal place. All data presented in the individual subject listings will be as recorded on the eCRF.

Individual weekly mean values will be calculated to one decimal place and summary statistics presented per the above quoted convention.

LS means and 95% CIs will be quoted to 2 decimal places. P-values will be quoted to 3 decimal places and p-values < 0.001 will be presented as p<0.001.

6.3.6 Data Displays

All clinical data tabulations, figures and listings will be generated as individual Rich Text Format (.rtf) files using SAS (Version 9.4 or higher)¹. Data summaries, statistical analyses and graphical analyses will be reported within Section 14 of the CSR and individual subject data listings within Appendix 16.2 of the CSR. Specifications (shells) for Tables, Figures and Listings will be provided as a separate document.

Subject disposition, baseline characteristics, demographic data, treatment exposure, compliance, medical history, concomitant medication, and adverse event data will be presented by treatment group and overall.

Other safety and efficacy data will be presented by treatment group only.

Treatment group labels will be displayed as follows:

NYX-2925 50 mg	Placebo
(N=XX)	(N=XX)

Listings will be sorted in the following order: treatment group, subject, parameter, and visit unless otherwise stated. All data will be listed. For some listings, subjects who were not randomized will be presented but will be displayed after the randomized treatment groups.

6.4 Subject Disposition

Subject disposition will be summarized as follows:

- The number of subjects, who entered the study, were randomized and who are in each analysis population will be summarized by treatment group and overall.
- *The number of subjects who failed screening and the reasons for failure will be tabulated for all subjects.
- The number of subjects who were not randomized and the reasons subjects were not randomized will be tabulated for all subjects.
- The number of early withdrawals and the reasons for withdrawal will be tabulated by treatment group and overall.
- The number of subjects who completed the study will also be tabulated by treatment group and overall.

*For participants who were re-screened, reason for screen failure will be taken from the most recent screening attempt. Data from both attempts will be listed.

6.5 Protocol Deviations

Protocol deviation categories will be tabulated by treatment group and classification (Major, Minor) for the Safety Population. Additionally, COVID-19 related protocol deviations will be identified. A listing of protocol deviations will be provided within Appendix 16.2 of the CSR.

6.6 Baseline Comparability

Comparability of treatment groups with respect to subject demographics and baseline characteristics will be assessed in a descriptive manner.

Standard continuous or categorical variable summaries will be presented by treatment group and overall, for the following variables, for the Safety Population.

Demographic Data

- Age at Informed Consent (years)
- Sex (Male/Female)
- Ethnicity
- Race, where more than one race is selected the participant will be presented under the 'Multiple races' category in the summary but each selected race will be identified in the listing.

Baseline Characteristics

- Weight at Screening (kg)
- Height at Screening (cm)
- BMI at Screening (kg/m²)
- Childbearing Potential (for female subjects only)

Clinical Characteristics

- Discontinuation of prior analgesic medications at Baseline (Yes/No/NA)
- Duration of DPN at Baseline (years)
- Duration of Painful DPN at Baseline (years)
- Patient Global Impression of DPN Severity
- Neurological Examination at Baseline (Normal/Abnormal, Not Clinically Significant [NCS], Abnormal, Clinically Significant [CS])

6.7 Medical History

Separate tabulations of prior and ongoing conditions at Screening will be presented by treatment group and overall, for the Safety Population. A listing of all the medical conditions for all subjects in the Safety Population will also be provided.

6.8 Prior and Concomitant Medications

Separate tabulations will be produced for prior and concomitant medications presented by treatment group and overall, for the Safety Population. For reporting purposes, prior medications are defined as all medications taken within 30 days of the Screening visit but stopping before the date of first dose of study drug. Concomitant medications are defined as medications taken on or after the date of first dose of study drug, including medications initiated prior to the first dose of study drug and continuing after first dose of study drug. Medications for which a stop date is not recorded will be designated ongoing at end of study. Prior and concomitant medications will be summarized using Anatomic Therapeutic Chemical (ATC) Level 3 and Preferred Name.

6.9 Exposure to Study Drug

Extent of exposure (number of days of exposure to study drug) will be presented by treatment group for the Safety Population.

6.10 Treatment Compliance

Treatment compliance, calculated as defined in Section 6.2.9, will be presented by treatment group per visit interval (Visit 2 to Visit 4, Visit 4 to Visit 5, and Visit 5 to Visit 6) for the Safety Population.

6.11 Efficacy Analyses

All statistical tests will be performed using a two-tailed 5% overall significance level, unless otherwise stated. All comparisons between treatments will be reported with 95% confidence intervals (CI) for the difference, unless otherwise stated.

6.11.1 Primary Endpoint

The primary efficacy endpoint is the change from baseline to Week 12 in the weekly mean of the NRS score assessing average pain intensity related to DPN in the past 24 hours.

The hypothesis that will be tested is as follows:

$$H_0 = \mu_{NYX,50 \, mg} - \mu_{placebo} = 0$$
 versus $H_1 = \mu_{NYX,50 \, mg} - \mu_{placebo} \neq 0$

Where $\mu_{NYX,50 mg}$ denotes the mean change from baseline to Week 12 in the weekly mean of the NRS score in the NYX-2925 50 mg treatment group,

And $\mu_{placebo}$ denotes the mean change from baseline to Week 12 in the weekly mean of the NRS score in the placebo group.

6.11.1.1 Estimand

The treatment-policy estimand will allow estimation of the improvement (reduction) from Baseline in the weekly mean of the daily NRS score in all subjects, irrespective of early discontinuation from treatment.

The following four attributes describe the estimand that will be used to define the treatment effect of interest for the primary efficacy analysis:

- 1. Population = Subjects meeting the protocol-specified inclusion/exclusion criteria, who received at least one dose of study drug and who have at least one post-baseline assessment of the pain intensity NRS.
- 2. Subject-level outcome = Change from baseline in the weekly mean of the daily NRS score assessing average pain intensity in the past 24 hours
- 3. Intercurrent event handling = An intercurrent event is defined as discontinuation of study drug due to an AE or lack of efficacy prior to Week 12 (where Action Taken with Study Drug (following AE) = "Study Drug Withdrawn" or Primary Reason for Withdrawal = "Adverse Event" or "Lack of Efficacy"). Missing data will not be imputed, and the missing values will be assumed to follow the missing-at-random (MAR) mechanism.
- 4. Population-level summary measure = Difference in least squares (LS) mean change from baseline in the weekly mean of the daily NRS score at Week 12, comparing NYX-2925 50 mg QD to placebo.

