#### Treatment Period: Week 12/Visit 6 or Early Termination Visit

During Week 12 (Visit 6) or Early Termination Visit, subjects will return to the clinic for assessment of compliance with study drug and rescue medication use. The appropriate use of study drug and rescue medication will be assessed by inventory of the returned study drug and rescue medication, as well as by subject interview. Subjects will return the study-issued handheld device and other materials to the study site. Pain diary compliance will be reviewed by the study staff. Adverse events will be assessed by asking the subjects a nonleading question. Misuse and abuse-related events will be assessed using MADDERS (Analgesic Solutions, Wayland, MA).

Use of concomitant medications will be documented. Additional procedures during Visit 6/Early Termination Visit will include S-STS and vital signs (blood pressure and pulse after sitting or lying supine for at least five (5) minutes). Body weight will be measured, a brief physical examination performed, and ECG would be conducted. Blood (8 hour fast) samples will be collected for hematology, serum chemistry, HbA1c, and urine sample will be collected for urinalysis testing. Female subjects of childbearing potential will be tested for pregnancy using a local urine testing kit. Subjects will a undergo drug screens using a local urine testing kit.

The following scales will be completed at the Week 12 (Visit 6)/Early Termination Visit: BPI-DPN, PGI-C, QOL-DN, PCS and S-STS.

A safety follow-up telephone call will be made to the subject within 7-10 days and then approximately 30 days after week 12/final visit to assess for any AE/SAE closure and any newly reported SAEs.

The schedule of assessments is provided in Table 3.

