Kandomize eligible subjects		X				
Dispense study drug		Х		Х	Х	
First dose of study drug (in the clinic)		Х				
Confirm daily study drug dosing in past 24 hours each morning p		Х	Х	Х	Х	Х
Return study drug and assess compliance m				Х	Х	Х
Pain Catastrophizing Scale (PCS)		Х				X
Brief Pain Inventory for Diabetic Peripheral Neuropathy (BPI- DPN)		Х		Х		Х
Norfolk Quality of Life Questionnaire – Diabetic Neuropathy (QOL-DN)		Х		Х		X
Patient Global Impression of Severity (PGI-S)	Х	Х				
Patient Global Impression of Change (PGI-C)				Х	Х	Х
Sheehan-Suicidality Tracking Scale (S-STS)	Х	Х	$\mathbf{X}^{w}$	Х	Х	Х
Misuse, Abuse, and Diversion Drug Event Reporting System ® (MADDERS) r			Х	Х	Х	Х
Concomitant medications	Хq	Х	Х	Х	Х	Х
Adverse events S	Х	Х	Х	Х	Х	Х
Safety follow-up calls						X x

Clin	ical Protocol Amendment #7 Masked NYX-2925-2008 25 June 202
a)	Subjects will discontinue all concomitant analgesic medications taken for pain related to diabetic peripheral neuropathy. Duration of the period will depend upon the analgesic(s) being discontinued, not to exceed 4 weeks. Subjects not taking any concomitant analgesic medications at Visit 1 may directly begin Week -1 of the Screening Period.
(q	ET=Early Termination. Subjects who prematurely discontinue randomized treatment will have Week 12 procedures performed. Diary completion ends the night before the Week 12 visit.
c)	Informed consent includes an additional consent for inclusion in a secure, proprietary, research subject database to screen for protocol violators. The main informed consent document may be executed up to 30 days prior to the screening visit. The date the first screening related activity is completed will be considered the subject's screening date. If the subject does not complete the screening visit within 30 days of signing the informed consent document the subject must be reconsented.
(p	Verify subject still meets all inclusion criteria and does not meet any exclusion criteria.
e)	Review of these educational materials via the aLearn portal will be repeated for all subjects at each site-based visit, with the exception of the final visit. Training at Visit 3 is per Investigator discretion. An ongoing blinded data review (e.g., if pain score variability is increased on a subject or site level) will be conducted to monitor these metrics [Analgesic Solutions, Wayland, MA].

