### 12.6.1.1. Primary Efficacy Analysis

The primary efficacy analysis will be performed based on the modified Intent-to-Treat population.

Aptinyx Confidential

The primary efficacy endpoint is the change from baseline in the weekly mean of the daily NRS score assessing average pain intensity in the past 24 hours. The primary efficacy analysis will evaluate the treatment-policy estimand in the modified Intent-to-Treat population. The treatment-policy estimand combines the improvement (reduction) from Baseline in the weekly mean of the daily NRS score and not discontinuing treatment early due to an AE or lack of efficacy through Week 12.

The following four attributes describe the estimand that will be used to define the treatment effect of interest for the primary efficacy analysis:

- 1. Population = Subjects meeting the protocol-specified inclusion/exclusion criteria, who received at least one dose of study drug and who have at least one post-baseline assessment of the pain intensity NRS.
- 2. Subject-level outcome = Change from baseline in the weekly mean of the daily NRS score assessing average pain intensity in the past 24 hours
- 3. Intercurrent event handling = An intercurrent event is defined as discontinuation of study drug due to an AE or lack of efficacy prior to Week 12. For the analysis, baseline Observation Carried Forward (BOCF) imputation will be used to impute data for visits after a patient has discontinued randomized treatment due to either of these reasons (even if data is present).
- 4. Population-level summary measure = Difference in least squares mean change from baseline in the weekly mean of the daily NRS score at Week 12, comparing each dose of NYX-2925 to placebo.

Any missing data at Week 12 that are not preceded by an intercurrent event (i.e., discontinuation of study drug due to AE or lack of efficacy) will remain as missing.

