6.2.17.2 Post-Baseline Weekly Mean NRS Scores

Weekly Mean NRS Scores for Week 12 (and prior weeks) will be obtained based on the subject's actual Week 12 visit date. If the subject's Week 12 visit date is within Day 80 to Day 88, then the 7th NRS score for Week 12 will be the corresponding NRS score on the day before the subject's Week 12 visit date, and the 6th to 1st NRS score for Week 12 will be obtained backwards from this. Thus, the corresponding NRS scores on the last 7 days prior to Week 12 actual visit date will be used for Week 12. Consequently, the Week 11 NRS scores will be obtained by counting 7 days backwards from the 1st NRS score for Week 12, Week 10 NRS scores will be obtained by counting 7 days backwards from the 1st NRS score for Week 11 and continuing up to Week 1. If the subject's actual Week 12 visit date is beyond Day 88, then the corresponding NRS score on the day before Day 88 (i.e., Day 87) will be used as the 7th NRS score for Week 12, and the 6th to 1st NRS score will be obtained backwards from this and continuing for each week from Week 11 to Week 1. Meanwhile, if the subject's actual Week 12 visit date is earlier than Day 80, then no Week 12 data will be identified.

Timing of Week 12 Visit	Reference Day (NRS)
Day 80 to Day 88	Count backwards from day before Week 12 visit
Day 80 to Day 88	(Week 12 study day -1)

Day 89+	Count backwards from Day 87 only	
Earlier than Day 80	No Week 12 data identified	

For subjects that withdraw early or have missing data such that they do not have any data that would fall into the Week 12 windowing, their last non-missing diary day will serve as the anchor; weeks will be counted backwards in 7-day intervals from the last day. For the week ending with this anchor day, study week will be assigned such that the majority of days fall in the nominal week. For example, Week 11 is nominally day 71-77; if a subject's last value is on day 74, the majority of the resulting 7-day window working backwards would be in "Week 11", so their last week would be analyzed as "Week 11" and the subsequent intervals assigned descending weeks working backwards. The following table shows how the last interval will be assigned based on its last day.

Timing of Last Non-Missing Diary	Assigned Week
	(from which to count backwards)
Day 1 to Day 10	Week 1
Day 11 to Day 17	Week 2
Day 18 to Day 24	Week 3
Day 25 to Day 31	Week 4
Day 32 to Day 38	Week 5
Day 39 to Day 45	Week 6
Day 46 to Day 52	Week 7
Day 53 to Day 59	Week 8

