6.11.1.2 Primary Efficacy Analysis

A restricted maximum likelihood (REML)-based mixed model for repeated measures (MMRM) will be utilized to analyze the change from baseline to Week 12 in the weekly mean of the NRS score assessing average pain intensity related to DPN in the past 24 hours.

The MMRM model will have site, treatment group, week, baseline NRS score, and treatment-by-week interaction as terms in the model. The unstructured covariance (UN) will be utilized as the within-subject covariance structure in the event that the model fails to converge using the UN, the covariance structure among Toeplitz (TOEP), first-order autoregressive [AR(1)], and compound symmetry (CS) for which the model converges and yields the least corrected Akaike's information criterion (AICC) will be used. The Kenward-Roger degrees of freedom correction will also be used for this analysis.

The estimate of the treatment difference at Week 12 and standard error (SE) will be derived from this model. Observed NRS scores at baseline and at each week, as well as their change from baseline at each week will be presented by treatment group. The LS means, corresponding SEs, and 95% CI for each treatment group, as well as the estimate, corresponding SE, and p-value of the treatment difference in LS means at each week will be presented.

The following is the sample SAS code that will be used for this analysis:

```
PROC MIXED DATA= DATAIN;

CLASS USUBJID TREATMENT WEEK SITE;

MODEL CFB = TREATMENT WEEK SITE TREATMENT*WEEK BASELINE / DDFM=KR;

REPEATED WEEK / SUBJECT=USUBJID TYPE=UN;

LSMEANS TREATMENT*WEEK / CL DIFF;

RUN;
```

A line plot showing the LS means and 95% CIs of the weekly mean NRS scores from Week 1 through Week 12 for each treatment group will be presented.

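### The primary estimand is labelled treatment-policy, but with no pain diary after early termination and an MMRM under MAR, the analysis mainly estimates the effect had subjects stayed on treatment

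*SAP*

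**What the plan says.** SAP 6.11.1.1 describes a treatment-policy estimand, meant to give the improvement in weekly mean pain "in all subjects, irrespective of early discontinuation from treatment". Its third attribute defines the intercurrent event as stopping study drug for an adverse event or lack of efficacy before Week 12. It names no strategy for that event and adds only: "Missing data will not be imputed, and the missing values will be assumed to follow the missing-at-random (MAR) mechanism". SAP 6.11.1.2 fits an MMRM to the available weekly means, and "The estimate of the treatment difference at Week 12 and standard error (SE) will be derived from this model".

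On data collection, Protocol Table 3 footnote b states: "Subjects who prematurely discontinue randomized treatment will have Week 12 procedures performed. Diary completion ends the night before the Week 12 visit". Protocol 6.1 says of the Week 12/ET visit: "Subjects will return the study-issued handheld device and other materials to the study site". After it, only the safety telephone calls are scheduled.

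On weekly scores, SAP 6.2.17.2 says that "if the subject's actual Week 12 visit date is earlier than Day 80, then no Week 12 data will be identified". For early withdrawals, "their last non-missing diary day will serve as the anchor; weeks will be counted backwards in 7-day intervals from the last day", and the accompanying table assigns such subjects Week 11 at the latest.

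Protocol 12.6.1.1 used the same label with baseline observation carried forward (BOCF), which would have overwritten even scores that had been observed after discontinuation. SAP section 9 item 2 discloses the move from BOCF to MAR. SAP 6.11.1.3.1 plans a control-based pattern-mixture analysis as a sensitivity analysis.

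**The concern.** A treatment-policy effect counts pain as it is at Week 12, whether or not the subject is still taking study drug. Estimating it needs pain scores after drug is stopped, or an imputation that represents being off drug. Here the diary stops at the ET visit, so the only possible off-drug scores are those between the last dose and that visit. MAR then fills the gap from the subject's own earlier scores and the later scores of subjects in the same arm, who are mostly still on treatment. That describes what would have happened had the subject continued.

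SAP section 9 reports that the handling changed but not that the quantity being estimated changed with it, and the label stayed. The primary result would then carry a claim about all subjects regardless of discontinuation that the design cannot support.

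**Working it through.** **1. The plan's own figure.** From SAP section 4: difference 0.73, SD 1.7, two-sided 0.05, 80% power, 15% drop-out; 1:1 allocation from SAP section 5.

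- n per arm = 2 × (1.96 + 0.8416)² × 1.7² / 0.73² = 85.1, rounded up to 86.
- 86 / 0.85 = 101.2, rounded up to 102 per arm, total 204.
- With 0.85 × 102 = 86.7 evaluable per arm, t-test power is 80.3%.

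The stated 204 reproduces. The sample size is not in question.

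**2. What is observed.** Take a subject who stops drug and has the ET visit before Day 80. The last diary entry is the night before, the device is returned, and the last weekly mean is at most Week 11. No Week 12 score exists. At 15%, about 0.15 × 102 = 15 subjects per arm are in this position. This treats the whole drop-out figure as treatment discontinuation, which is an assumption.

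**3. Size of the gap, drug arm only.** Assume 0.73 is the on-treatment effect and let k be the share of it that drug-arm dropouts keep at Week 12. The difference regardless of discontinuation is 0.73 × (0.85 + 0.15k).

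| k | Difference |
|---|---|
| 0 | 0.62 |
| 0.5 | 0.68 |
| 1 | 0.73 |

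**4. Direction.** Let Ld and Lp be the points by which drug and placebo dropouts end worse than MAR projects. The difference is 0.73 − 0.15·Ld + 0.15·Lp.

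- Ld = 0.73, Lp = 0: 0.62
- Ld = 0.73, Lp = 0.73: 0.73
- Ld = 0, Lp = 0.73: 0.84

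The documents do not say which applies.

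**5. Does MAR return the on-treatment value?** This was simulated with SD 1.7, drop-out depending on the last observed score, and drug-arm dropouts losing the whole effect.

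| Setting | On treatment | Regardless of discontinuation | MAR | Control-based |
|---|---|---|---|---|
| AR(1) correlation 0.80 to 0.95, drop-out 14–16% | 0.73 | 0.62–0.63 | 0.72–0.73 | 0.66, 0.68, 0.70 at 0.80, 0.90, 0.95 |
| Constant correlation 0.7, drop-out 13.6% placebo, 11.2% drug | 0.741 | 0.659 | 0.742 | not run |

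In the second row the gap is 0.741 − 0.659 = 0.082, which matches 0.112 × 0.73. In both settings MAR recovers the on-treatment effect. The control-based estimate lies between the two targets, because the placebo regression conditions on the subject's own earlier scores and so carries some of the earlier benefit forward.

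**6. The control-based sample code (SAP 6.11.1.3.1).**

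- The `MNAR` statement names `NRS1_Week1`; every other statement uses `NRS_Week1`.
- `LSMEANS TREATMENT TREATMENT*WEEK` also outputs the main-effect difference. In that row `WEEK` and `_WEEK` are both missing, so it passes `WHERE=(WEEK=_WEEK)`.
- The differences are then combined `BY TREATMENT` only. That puts (12 weekly + 1 main effect) × 20 imputations = 260 rows into one group and gives no Week 12 difference, although the text below the code asks for one at each week.
- With the variable name corrected and those rows pooled, a true Week 12 effect of 0.73 would appear as 0.73 × 78/144 = 0.40 if it builds linearly over 12 weeks, or 0.73 × 10.5/12 = 0.64 if it is complete by Week 4. The main effect is the mean of the weekly differences, so including it leaves these values unchanged.

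**The case against.** The strongest reply is that this is a matter of labelling and the SAP is better protected than the label suggests. Section 9 discloses the change from BOCF to MAR. The control-based table already follows the primary table. The tipping-point analysis (SAP 6.11.1.3.2) makes drug-arm dropouts progressively worse than placebo until significance is lost, and it runs exactly when a positive claim could be overstated. Missing Week 12 pain or PGI-C counts as non-response in the responder analyses. No conclusion text exists yet, so nothing has been misreported.

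All of that is true, but none of it names the quantity the primary analysis estimates. The sensitivity analyses are presented as tests of MAR, not as estimates of the effect that 6.11.1.1 claims. The control-based analysis is itself one assumption: it models placebo dropouts as if they had completed. It also cannot represent analgesics resumed after ET, since Table 3 footnote k bars restarting them only until after the Week 12 visit.

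The objections to the magnitude partly stand. The SAP's intercurrent event covers only adverse events and lack of efficacy, whereas the 15% may include other reasons, so 0.73 − 0.62 = 0.11 is a worst case for the defined event under step 3. The figures in step 4 are scenarios, not bounds: if drug dropouts ended 0.73 worse and placebo dropouts 0.73 better than projected, the formula gives 0.51.

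On the code, it is marked as a sample, the surrounding prose asks for the right output, and a statistician programs the table independently. A wrong published figure is therefore less likely. The text nevertheless says this code will be used, and it belongs to the planned analysis closest to the stated estimand.

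**Conclusion.** The concern holds. The label in SAP 6.11.1.1 does not match the data collected or the estimator; the MMRM under MAR mainly targets a hypothetical effect under continued treatment. The word mainly is needed because entries between last dose and ET are kept where they exist, and a discontinuer whose visit falls on Day 80 or later can have a Week 12 score.

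The primary estimate, confidence interval, p-value and sample size stand. The size and direction of the gap cannot be learned from this design. The illustrative values of 0.62, 0.73 and 0.84 rest on 15% drop-out in both arms, on reading 0.73 as the on-treatment effect, and on assumed outcomes after stopping. The correction should be made, because it settles what the primary result may be said to show.

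**What to change.** 1. In SAP 6.11.1.1, replace the treatment-policy label with a stated hypothetical strategy for treatment discontinuation. Word the primary conclusion to match, and say in section 9 item 2 that the strategy changed as well as the handling of missing data.
2. Report the control-based analysis (6.11.1.3.1, Table 14.2.1.1.2) beside the primary result as one assumption-based estimate of the effect regardless of discontinuation. State that it assumes placebo-like pain after drug is stopped and MAR within placebo, and that no diary after ET exists to check either.
3. Correct the sample code: use `NRS_Week1` in the `MNAR` statement, keep only the `TREATMENT*WEEK` differences, then sort and combine them `BY WEEK`.

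The cost is some SAP wording and a few lines of code, with no new data, model or table. The claim attached to the primary result becomes narrower. Keeping the treatment-policy label is also coherent, but it would need a different primary estimator, such as the control-based one, or a protocol change to collect diaries after discontinuation. Either is a larger change.
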